## **Treatment-Free Follow-up ALT Management**

All participants not on NUC treatment will enter TFFU period after completion of study treatment, in which they will undergo close safety monitoring. The proportion of participants who achieve HBsAg loss or are able to remain off NUC therapy during TFFU period will be assessed. Table 7 provides guidance for initiating commercially approved NUC treatment, in participants who experience rebound of HBV DNA and ALT levels. Any deviation from the table should be discussed in advance with medical monitor.

If unscheduled visits are required for ALT monitoring, a clinical assessment of the participant should be performed. The assessment should include a physical examination, evaluation of the participant's mental status and the following laboratory tests:

- Laboratory parameters: serum ALT and AST, total and direct bilirubin, GGT, INR, serum albumin, plasma HBV DNA, quantitative HBsAg, PBMC for immune profiling, and alcohol screen.
- At the initial confirmatory visit, collect serology for HDV, HAV IgM, HCV, and HEV.

Participants with HBV DNA  $\leq$  LLOQ and ALT elevation/flare meeting any of the below table criteria should be evaluated for alternative liver disease etiologies by the investigator and in discussion with the medical monitor. Liver biopsy may be collected at the investigator's discretion.

Participants with HBV DNA > LLOQ and ALT elevation/flare should be managed according to the table below:

Table 7. Starting Commercial NUC Treatment Criteria

Liver Toxicity Parameters	Action
Confirmed ALT $\geq$ 10 × ULN with no evidence of hepatic toxicity, as defined below.	Initiate NUC treatment and monitor weekly until ALT $< 5 \times ULN$ , and every 2 weeks until ALT $< 2 \times ULN$ , or more frequently if clinically indicated.
ALT $\geq$ 5 × ULN without evidence of hepatic toxicity, as defined below	ALT should be evaluated every 2 weeks or more frequently as clinically needed, until ALT < 2 × ULN.
Confirmed ALT > ULN with evidence of hepatic toxicity, defined as any one of the following confirmed laboratory abnormalities:  • Total bilirubin > 2 × nadir AND > 2.5 mg/dL in the absence of Gilbert's disease  • Elevated INR > 0.5 above nadir AND > ULN  • Abnormal serum albumin > 1 g/dL decrease from baseline	Initiate NUC treatment and monitor weekly or more frequently if clinically indicated until return to baseline levels or within normal reference range. Liver biopsy may be considered if appropriate for participant management.
Confirmed, HBV DNA > 20,000 IU/mL (HBeAg positive) or > 2,000 IU/mL (HBeAg negative) and persistent ALT > ULN without evidence of hepatic toxicity, as defined above, for > 8 weeks	Initiating NUC treatment may be considered in discussion with the medical monitor.

ALT = alanine aminotransferase; DNA = deoxyribonucleic acid; HBeAg = hepatitis B e antigen; HBV = hepatitis B virus; NUC = nucleos(t)ide(s); ULN = upper limit of normal

## 8. STATISTICAL CONSIDERATIONS

## 8.1. Analysis Objectives and Endpoints

## 8.1.1. Analysis Objectives

The primary objectives of this study are as follows:

- To evaluate the safety and tolerability of study treatment(s)
- To evaluate the efficacy of study treatment(s) as measured by the proportion of participants who achieve functional cure, defined as HBsAg loss and HBV DNA < LLOQ at FU Week 24

The secondary objectives of this study are as follows:

- To evaluate the proportion of participants with HBsAg loss with and without anti-HBsAg seroconversion during the study
- To evaluate in participants with CHB who are HBeAg positive at baseline, the proportion of
  participants who achieve HBeAg loss with and without anti-HBeAg seroconversion during
  the study
- To evaluate the proportion of participants who remain off NUC treatment during FU
- To evaluate the proportion of participants experiencing HBV virologic breakthrough during study treatment(s)

## 8.1.2. Primary Endpoint

The primary efficacy endpoint is the proportion of participants who achieve functional cure, defined as HBsAg loss and HBV DNA < LLOQ at FU Week 24.

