The loss of HBsAg, accompanied by seroconversion to anti-HBsAg, is the accepted endpoint for anti-HBV therapy endorsed by the American Association for the Study of Liver Diseases, the European Association for the Study of the Liver, and the Asian Pacific Association for the Study of the Liver allowing for cessation of therapy {European Association for the Study of the Liver (EASL) 2012, European Association for the Study of the Liver (EASL) 2017, Lok 2009, {Sarin 2015, Terrault 2016}. Clearance of HBsAg has been associated with improvements in liver histology, including the reversal of cirrhosis, a decreased risk of HCC, and prolonged survival, and is considered evidence of a functional cure {Benias 2011, Fattovich 1998, Kim 2013}. Nucleos(t)ide (NUC) analogs are the standard-of-care for CHB treatment, providing durable suppression of viral replication that results in long-term clinical benefits with a reduced risk of liver complications {Dienstag 2003, Liaw 2011, Lok 2013}. However, treatment with NUCs rarely results in clearance of HBsAg {Kwon 2011}. Thus, new treatment options that enhance rates of HBsAg clearance are needed; such treatments will allow patients to discontinue life-long oral antiviral (OAV) therapy and provide a finite-duration treatment option for a functional cure. A finite therapy is expected to be applicable to a broader population of those chronically infected with HBV, including immunotolerant patients who are currently untreated.

The host immune response to HBV infection plays a pivotal role in whether acute infection is resolved or becomes chronic. Individuals who are able to clear HBV infection spontaneously following an acute infection display a vigorous, polyclonal, HBV-specific cluster of differentiation (CD)8+ and CD4+ T-cell response {Rehermann 2005}. In contrast, CHB is associated with a limited and dysfunctional CD8+ T-cell response, as well as impaired natural

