### 3. STUDY DESIGN

### 3.1. Endpoints

The primary endpoint of this study is as follows:

 The proportion of participants who achieve functional cure, defined as HBsAg loss and HBV DNA < LLOQ at FU Week 24

The secondary endpoints of this study are as follows:

- The proportion of participants with HBsAg loss with and without anti-HBsAg seroconversion during the study
- The proportion of participants with HBeAg loss with and without anti-HBeAg seroconversion during the study in participants with CHB who are HBeAg positive at baseline
- The proportion of participants who remain off NUC treatment during FU
- The proportion of participants experiencing HBV virologic breakthrough during study treatment(s) as defined in Section 2

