### 3.2.1. Changes to Study Design

Nivolumab dosing was stopped by Gilead based on emerging safety data from this study, other studies, and pertinent patient and prescriber insights {Cohen C. 2020}. As the study had completed enrollment and all participants were in treatment when the decision was made to stop nivolumab administration, the following measures were implemented:

- Stop further nivolumab administration for all study participants across all cohorts.
- Continue treatment with VIR-2218 and SLGN through Week 36 for Cohorts 1 and 2 (Group A).

- Discontinue all study treatment for Cohort 2 Group B participants with next follow-up visit being EOT for those still in treatment period.
- Stop all sample collections related to nivolumab.
- NUC therapy cessation is no longer required for our NUC treated patients (Cohort 1).

GS-US-465-4439: Study Design Schema\* Figure 1.

= intravenous; NUC = nucleos(t)ide(s); PO = oral; Q4W = every 4 weeks; QD = once daily; QW = every week;

SLGN = selgantolimod; SC = subcutaneous; TAF = tenofovir alafenamide

- Viremic participants who meet criteria to initiate NUC treatment will receive TAF 25 mg once daily for up to 36 weeks ಡ
  - during the study.

    b SLGN dosed while fasting once a week, on the same day, for 24 weeks.
    - c Participants will continue to receive TAF per Section 3.5.
- \* NOTE: Nivolumab dosing was stopped in this study and all treatments in Cohort 2 Group B were discontinued. This was a sponor decision based on a benefit risk assessment on the use of nivolumab in HBV cure. Rationale is provided in Section 1.3.1.

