### 3.5. Follow-up Period

At the end of treatment, all participants will enter the FU period.

- All participants not on TAF treatment at EOT will enter a TFFU period.
- Participants who are on TAF treatment will continue TAF treatment over the duration of study follow-up.
- Participants who initiated TFFU prior to the approval of this amendment and stopped NUC
  treatment may continue off NUCs after discussion between participant and investigator on
  the benefits and risks of continuing off NUCs in TFFU. Those who decide to restart NUCs
  would initiate commercial NUC treatment.

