### 4.2. Inclusion Criteria

Participants must meet all of the following inclusion criteria to be eligible for participation in this study:

- 1) Must have the ability to understand and sign a written informed consent form (ICF), which must be obtained prior to initiation of study procedures
- 2) Adult male and nonpregnant, nonlactating female participants, 18 to 65 years (19-65 years of age in Republic of Korea) of age inclusive based on the date of the screening visit
- 3) Documented evidence of chronic HBV infection (eg, HBsAg positive for more than 6 months) with detectable HBsAg levels (> 1.5 log10 IU/mL) at screening
- 4) Screening electrocardiogram (ECG) without clinically significant abnormalities and with QTcF interval (QT corrected using Fridericia's formula) ≤ 450 msec for males and ≤ 470 msec for females.
- 5) Females of childbearing potential (as defined in Appendix 11.4) must have a negative serum pregnancy test at screening and a negative urine pregnancy test at baseline prior to enrollment
- 6) Male and female participants of childbearing potential who engage in heterosexual intercourse must agree to use protocol-specified method(s) of contraception as described in Appendix 11.4. Must be willing and able to comply with all study requirements.

Participants in Cohort 1 should meet the following additional criteria to be eligible to participate in this study:

7) Have been on a commercially available HBV NUC treatment(s) (ie, TAF, TDF, entecavir, adefovir, lamivudine, telbivudine, either as single agents or in combination) with no change in regimen for 3 months prior to screening and willing to initiate TAF 25 mg.

- 8) Have a historical HBV DNA < LLOQ, measured at least once at local laboratory, 6 or more months prior to screening.
- 9) HBV DNA < LLOQ by central laboratory at screening

Participants in Cohort 2 should meet the following additional criterion at screening to be eligible to participate in this study:

10) HBV DNA > 2000 IU/mL (HBeAg negative) and HBV DNA > 20,000 IU/mL (HBeAg positive)

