## 7.7.5. ALT Elevation or Flare Management on Treatment and Treatment-Free Follow-up

## **On-Treatment ALT Management**

Participants with on-treatment serum ALT elevation  $> 2 \times$  nadir or  $> 2 \times$  baseline value and  $\ge 5 \times$  ULN, with or without associated symptoms should be managed according to the guidance below.

All elevated serum ALT should be confirmed as soon as possible and ideally within 3 days of receipt of results. During the visit, a clinical assessment of the participant should be performed. The assessment should include a physical examination, evaluation of the participant's mental status, and the following laboratory tests:

- Laboratory parameters: serum ALT and AST, total bilirubin, GGT, INR, and serum albumin, alcohol screening
- If the ALT elevation is confirmed, the central clinical laboratory will conduct reflex testing for plasma HBV DNA, serology for HBV (HBsAg, HBsAb, HBeAg and HBeAb), HDV, hepatitis A virus (HAV) IgM, HCV, and HEV
- Liver biopsy may be collected for participants meeting Hy's law (ALT >  $3 \times ULN$  and Total Bilirubin >  $2 \times ULN$ ; AST >  $3 \times ULN$  and Total Bilirubin >  $2 \times ULN$ ) with suspected DILI

Additional confirmatory tests such as HDV RNA, HDV IgM, and HEV RNA may be performed locally as per local regulations after further discussion with the Gilead's Medical Monitor.

Based on the results of the confirmatory tests, the following study treatment modifications are recommended (Table 6).

Table 6. Dose Modification and Monitoring

Liver Toxicity Parameters	Action
Confirmed, ALT $\geq 10 \times ULN$ without evidence of hepatic toxicity as defined below	Cohort 1: Hold VIR-2218 and SLGN treatment. Participant should be monitored weekly or more frequently if clinically indicated until ALT < 5 × ULN. Restarting VIR-2218 and/or SLGN treatment may be considered when ALT < 5 × ULN in discussion with the medical monitor. Study treatment should be restarted in line with the original assigned administration schedule.  Cohort 2: Initiate TAF 25 mg once daily and hold VIR-2218 and SLGN dose. Participant should be monitored weekly or more frequently if clinically indicated until ALT < 5 × ULN. Restarting VIR-2218 and/or SLGN treatment may be considered when ALT < 5 × ULN in discussion with the medical monitor. Study treatment should be restarted in line with the original assigned administration schedule.

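### After Amendment 2 the primary endpoint counts HBsAg loss on TAF and HBsAg loss off NUC alike as functional cure, so the Cohort 1 proportion cannot show off-treatment control

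*Supplement*

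**What the plan says.** **Endpoint.** Section 8.1.2 sets the primary efficacy endpoint as the proportion achieving "functional cure, defined as HBsAg loss and HBV DNA < LLOQ at FU Week 24". Section 3.1 reads the same way: "The proportion of participants who achieve functional cure, defined as HBsAg loss and HBV DNA < LLOQ at FU Week 24". The synopsis, Section 2 and Section 8.1.1 give the same two components and no condition on NUC use.

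**Follow-up.** Section 3.2.1 states: "NUC therapy cessation is no longer required for our NUC treated patients (Cohort 1"). Section 3.5 adds: "Participants who are on TAF treatment will continue TAF treatment over the duration of study follow-up". Section 3.4 allows TAF in Cohort 1 for up to 84 weeks, including the 48-week follow-up. Section 3.5 makes an exception for a group described as "Participants who initiated TFFU prior to the approval of this amendment and stopped NUC" treatment. They may remain off NUC after discussion with the investigator. Their number is not stated.

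**Entry.** Cohort 1 participants must be on a NUC and have "HBV DNA < LLOQ by central laboratory at screening" (Section 4.2, criteria 7 to 9).

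**NUC starts in Cohort 2.** In Section 7.7.5, Table 6 has an on-treatment rule: "Cohort 2: Initiate TAF 25 mg once daily and hold VIR-2218 and SLGN dose". Table 7 covers the start of a commercial NUC during follow-up.

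**Analysis.** Section 8.5.1 gives one proportion with a Clopper-Pearson interval per treatment cohort. Section 8.3.1.5 treats missing data as failure and is silent on NUC use. Remaining off NUC during follow-up is a separate secondary endpoint (Section 8.1.3).

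**The concern.** The protocol presents functional cure as the route to finite therapy. Section 1.1 says of the new options that "such treatments will allow patients to discontinue life-long oral antiviral (OAV) therapy and provide a finite-duration treatment option for a functional cure". Section 1.3.2 gives the aim of treatment-free follow-up as evaluating response after treatment has stopped.

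Under that scheme, suppressed, HBeAg-negative participants with HBsAg below 100 IU/mL at end of treatment were to stop NUC. HBeAg-negative participants who had lost HBsAg by then would therefore have been assessed off drug at FU Week 24. Amendment 2 removed that step, and the endpoint kept its name and its two components.

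At stake is what the headline result for Cohort 1, 40 of about 100 planned participants, can be taken to mean. A reader who sees a functional cure rate will take it as control without drug. For anyone still on TAF, the visit cannot show that.

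**Working it through.** The documents show no sample-size or precision figure to reproduce. The check is a reading of the rules against the visit calendar, followed by an illustration.

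**1. Is FU Week 24 inside TAF dosing?** Cohort 1 treatment lasts 36 weeks, so FU Week 24 is study Week 36 + 24 = 60. TAF may run to Week 36 + 48 = 84. Since 60 < 84, the primary visit falls within TAF dosing for anyone still on it.

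**2. What does each component add in Cohort 1?**

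| Component at FU Week 24 | Participant on TAF | Participant off NUC |
|---|---|---|
| HBsAg loss | Informative; under 1% on NUC alone (Section 1.5) | Informative |
| HBV DNA < LLOQ | Met at screening on a NUC and supported by TAF; adds little | Informative: shows control without drug |
| Label in the plan | Functional cure | Functional cure |

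The two columns answer different questions and enter one proportion.

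**3. How far could the label matter?** The inputs are n = 40 (planned Cohort 1 size, Section 3.3) and the exact method of Section 8.5.1. For x responders, the lower limit is the 0.025 quantile of Beta(x, n − x + 1) and the upper limit is the 0.975 quantile of Beta(x + 1, n − x). For x = 0 the lower limit is 0 and the upper is 1 − 0.025^(1/40) = 8.8%.

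Suppose, as an assumption, that 4 participants meet the composite. The plan reports 4/40 = 10.0% (2.8 to 23.7) whatever their NUC status. The proportion with no NUC depends on how many of the 4 were off it:

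| Responders off NUC | Off-NUC functional cure | Exact 95% CI |
|---|---|---|
| 4 | 10.0% | 2.8 to 23.7 |
| 2 | 5.0% | 0.6 to 16.9 |
| 1 | 2.5% | 0.1 to 13.2 |
| 0 | 0% | 0 to 8.8 |

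The reported figure is identical in all four rows. The last row is the extreme case.

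For other assumed totals with every responder on TAF, the plan would report:
- 1/40 = 2.5% (0.1 to 13.2)
- 2/40 = 5.0% (0.6 to 16.9)
- 8/40 = 20.0% (9.1 to 35.6)

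Each corresponds to 0/40 off NUC.

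**4. Cohort 2.** A participant who starts TAF under Table 6 and is on it at end of treatment continues it (Section 3.5). One who starts a commercial NUC under Table 7 had HBV DNA above LLOQ and an ALT elevation. Either could have HBV DNA < LLOQ at FU Week 24 because of the NUC, and no rule addresses this. HBsAg loss must still be present at that visit.

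**The case against.** **HBsAg loss is the hard part.** This stands. A reader might infer that suppressed HBV DNA on TAF will by itself be reported as cure. The definition does not support that, because both components are required and NUCs alone rarely clear HBsAg. Nor is the DNA component guaranteed on TAF: virologic breakthrough under NUC therapy is a secondary endpoint. The component discriminates weakly, which is a smaller claim than being met by design.

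**The definition does not have to include stopping.** Section 1.1 also treats HBsAg clearance as evidence of functional cure, and Section 1.5 describes stopping therapy as something the response permits. So no passage makes off-NUC status part of the definition. That weakens any claim that the endpoint is wrong as written. It does not answer the point that two different states share one label after the amendment.

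**Off-NUC status is already a secondary endpoint.** It is a separate proportion. Without a cross-tabulation it cannot show how many primary responders were off NUC.

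**The analysis is descriptive and a SAP may handle this.** No hypothesis test or control comparison is planned, and the cohorts are not pooled. No SAP is shown, and a tabulation by NUC status could sit there. The name and definition of the primary endpoint, however, are in the protocol.

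**Redefinition is costly.** Scoring protocol-directed TAF as failure, in an open-label study with enrolment complete, would be a debatable change and could leave the Cohort 1 primary result nearly uninformative. This stands, and is why the composite should be kept and reported.

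**The Cohort 2 route is narrow.** This stands too. A reader might infer that NUC rescue can manufacture cures. It can supply only the DNA component, and no frequency can be derived.

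**Conclusion.** The point holds in a limited form. After Amendment 2, the Cohort 1 primary proportion counts HBsAg loss on TAF and HBsAg loss off NUC alike as functional cure. For participants on TAF it is essentially an on-NUC HBsAg-loss rate, and the single proportion cannot show off-treatment control.

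The size is unknown. The documents give neither the number who stopped NUC before the amendment nor any expected response rate. The contrast of 10.0% (2.8 to 23.7) with 0% (0 to 8.8) assumes 4 responders in 40, all on TAF. It is an extreme case and should not be read as an estimate of bias. It would also be wrong to say that no Cohort 1 participant can show off-treatment control, since Section 3.5 lets some remain off NUC.

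The conclusion rests on the protocol alone. A SAP rule splitting the result by NUC status would reduce the problem but would not change the protocol's label.

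**What to change.** These changes concern analysis and labelling only. TAF management is untouched.

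1. In Sections 3.1, 8.1.2 and 8.5.1, keep the composite as collected and report it by NUC status between end of treatment and FU Week 24, each part with its exact 95% interval.
2. Reserve the term functional cure for participants who meet the composite with no NUC in that interval. Name the remainder HBsAg loss with HBV DNA < LLOQ on NUC.
3. State the denominators. The whole-cohort Full Analysis Set is suitable for both named outcomes, shown with the number of participants on and off NUC. Under the scheme in Section 1.3.2, stopping depended on end-of-treatment status, so a percentage among off-NUC participants alone would describe a selected group.
4. In Cohort 2, count participants who started a NUC and are on it at FU Week 24 as not having functional cure.
5. Section 5.4 requires concomitant medications to be recorded only up to 4 weeks after study treatment stops, whereas Section 6.7 reviews them throughout follow-up. Align the two so that commercial NUC use is captured to FU Week 24.
6. Reconcile the remaining treatment-free follow-up wording (the synopsis text on ALT management in that period, Section 1.3.2, and the FU Week 1 entry check in Section 6.7) with Sections 3.2.1 and 3.5.

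The cost is wording and one further table, plus confirmation that NUC dates are recorded through follow-up. The downside is real: Cohort 1 may contribute few or no participants to a functional cure claim.

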## 8.1.3. Secondary Endpoint

Secondary efficacy endpoints of this study are as follows:

- The proportion of participants with HBsAg loss with and without anti-HBsAg seroconversion during the study
- The proportion of participants with HBeAg loss with and without anti-HBeAg seroconversion during the study in participants with CHB who are HBeAg positive at baseline
- The proportion of participants who remain off NUC treatment during FU
- The proportion of participants experiencing HBV virologic breakthrough during study treatment(s)

## 8.2. Planned Analyses

## 8.2.1. Primary Analysis

The primary analysis will be conducted after all participants within each cohort have completed FU Week 24 or early terminated from the study prior to FU Week 24.

## 8.2.2. Final Analysis

The final analysis will be performed at the end of the study, after all participants have completed the study or early terminated from the study, outstanding data queries have been resolved or adjudicated as unresolvable, and the data have been cleaned and finalized.

